### 8.3.1.5 Subgroup Analysis

Subgroup analyses of the primary efficacy endpoint will be performed for each of the following subgroups:

- Age at screening (<18; ≥18 years)
- ppFEV1 at baseline (<70; ≥70 percentage points)
- SwCl at baseline (<30; ≥30 mmol/L)
- Sex (male; female)
- Geographic region (North America [including United States and Canada]; Rest of the World [including Europe, Israel, Australia, and New Zealand])

The MMRM used for the primary analysis of the primary estimand (8.3.1.3) will be used for the subgroup analyses, where the same model will be applied to each category of the subgroup. Note that for the subgroup analysis based on age, the term age at screening (<18 versus ≥18 years of age) will be removed from the MMRM. The adjusted means with 2-sided 95% CIs will be provided. Furthermore, the estimated treatment difference through Week 24 (estimated by averaging Weeks 16 and 24) in different categories within a subgroup will also be presented in a forest plot. Note: The results from the subgroup analyses should be interpreted with caution in the cases where sample sizes are small.

### 8.3.2 Analysis of Key Secondary Efficacy Variables

The tests for absolute change from baseline in SwCl through Week 24 (continuous variable) based on the FAS and the proportion of subjects with SwCl <60 mmol/L and SwCl <30 mmol/L through Week 24 based on the PFAS will be subject to multiplicity control. Note that the within-study analyses of the proportion of subjects with SwCl <60 mmol/L through Week 24 and the proportion of subjects with SwCl <30 mmol/L through Week 24 based on the FAS are Other Secondary Endpoints and are not subject to multiplicity control; analyses of these endpoints are described in 8.3.3.

#### 8.3.2.1 Definition of Variables

**Sweat chloride (SwCl):** The SwCl value at a given visit will be calculated as the mean of the non-missing sweat chloride measurements obtained on the left and right arms at that visit. If one of the two arm measurements at a time point is missing, the other will be used as the mean. A volume ≥15 µL is required for an accurate determination of sweat chloride. Any results reported as having volume <15 µL will be considered missing. Any sweat chloride values reported as

>160 mmol/L will be considered missing. Any sweat chloride values reported as <10 mmol/L will be imputed as 10 mmol/L.

### **8.3.2.2 Analysis Method**

#### **Absolute change from baseline in SwCl through Week 24:**

The estimand for the absolute change from baseline in SwCl through Week 24 is defined as the following:

- Treatment: VNZ/TEZ/D-IVA versus ELX/TEZ/IVA
- Population: Study population represented by inclusion and exclusion criteria
- Variable: Absolute change from baseline (after ELX/TEZ/IVA run-in) in SwCl through Week 24 (estimated by averaging Weeks 16 and 24)
- Handling of ICE: Same as the primary estimand (8.3.1.2)
- Population level summary: Difference in variable means between VNZ/TEZ/D-IVA and ELX/TEZ/IVA groups

The analysis of absolute change from baseline in SwCl through Week 24 will be based on an MMRM similar to the primary analysis of the primary estimand (8.3.1.3), with absolute change from baseline in SwCl at Day 15, Week 4, Week 16, and Week 24 as the dependent variable. The estimated treatment difference through Week 24 (estimated by averaging Weeks 16 and 24) will be presented along with the 2-sided 95% CI and *P* value. The estimated within-group change from baseline and treatment difference at each post-baseline visit, obtained from the model, will be provided. The estimated within-group change and its SE at each post-baseline visit will also be plotted by treatment group.

#### **Proportion of subjects with SwCl <60 mmol/L through Week 24 (pooled with data from Study 102):**

The estimand for the proportion of subjects with SwCl <60 mmol/L through Week 24 is defined as the following:

- Treatment: VNZ/TEZ/D-IVA versus ELX/TEZ/IVA
- Population: Pooled study population represented by inclusion and exclusion criteria
- Variable: Response defined as SwCl <60 mmol/L through Week 24 (estimated by averaging Weeks 16 and 24)
- Handling of ICE: Same as the primary estimand (8.3.1.2)
- Population level summary: Odds ratio comparing the response rates in VNZ/TEZ/D-IVA and ELX/TEZ/IVA groups

The response corresponding to SwCl <60 mmol/L at each visit through Week 24 in the PFAS will be analyzed using a generalized estimating equations (GEE) model. The model will include fixed categorical effects for treatment, age at screening (<18 versus ≥18 years of age), genotype group (F/MF, F/F, F/G, F/RF, TCR/non-F), visit, and treatment-by-visit interaction, with baseline ppFEV1 and baseline SwCl as continuous covariates. A logit link function and an unstructured working correlation matrix will be used in the GEE model. If the model estimation

does not converge, genotype group will be considered with three levels (F/MF, F/F, and Other) or removed from the model, and if non-convergence persists, an alternative covariance structure like compound symmetry will be used. The estimated odds ratio through Week 24 (estimated by averaging Weeks 16 and 24) along with the 2-sided 95% CI and *P* value will be presented. The estimates for each visit through Week 24 will also be presented. The number and proportion of subjects with SwCl <60 mmol/L at each post-baseline visit through Week 24 will be descriptively summarized by treatment group.

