### **7.2 Secondary Endpoints**

#### **7.2.1 Key Secondary Endpoints**

- Absolute change from baseline in sweat chloride (SwCl) through Week 24
- Proportion of subjects with SwCl <60 mmol/L through Week 24 (pooled with data from Study VX20-121-102)
- Proportion of subjects with SwCl <30 mmol/L through Week 24 (pooled with data from Study VX20-121-102)

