### **Proportion of subjects with SwCl <30 mmol/L through Week 24 (pooled with data from Study 102):**

The estimand and analysis will be similar to that for the pooled analysis of proportion of subjects with SwCl <60 mmol/L through Week 24.

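### The pooled sweat-chloride responder endpoints are summarised as an odds ratio of group response rates, but the adjusted logit GEE reports a covariate-conditional odds ratio

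*SAP*

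**What the plan says.** Protocol 7.2.1 lists "Proportion of subjects with SwCl <60 mmol/L through Week 24 (pooled with data from Study VX20-121-102") as a key secondary endpoint, with a matching <30 mmol/L endpoint. SAP 8.3.2.3 places both in the alpha-controlled hierarchy, after the SwCl change endpoint.

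For <60 mmol/L, SAP 8.3.2.2 sets out:

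- **Estimand summary:** "Population level summary: Odds ratio comparing the response rates in VNZ/TEZ/D-IVA and ELX/TEZ/IVA groups".
- **Model:** "A logit link function and an unstructured working correlation matrix will be used in the GEE model". Besides visit and treatment-by-visit terms, it adjusts for age group, genotype group, baseline ppFEV1 and baseline SwCl, the last two as continuous covariates.
- **Reported effect:** "The estimated odds ratio through Week 24 (estimated by averaging Weeks 16 and 24) along with the 2-sided 95% CI" and a P value.
- **Reported proportions:** "The number and proportion of subjects with SwCl <60 mmol/L at each post-baseline visit through Week 24 will be descriptively summarized by treatment group".

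For <30 mmol/L: "The estimand and analysis will be similar to that for the pooled analysis of proportion of subjects with SwCl <60 mmol/L through Week 24". The within-study versions (SAP 8.3.3.2) and the Week 52 versions (SAP 8.3.4.2 and 8.5.2) use the same kind of model. Nowhere does the SAP say whether the odds ratio is meant to be marginal or conditional on covariates, and it plans no step that turns the fitted model into group response rates.

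**The concern.** A group's response rate is an average over everyone in that group, so an odds ratio comparing two such rates is most naturally marginal. GEE is population-averaged over a subject's repeated visits, but its treatment coefficient is still conditional on the covariates in the model. Odds ratios are non-collapsible: adjusting for a strong predictor of response moves a non-null odds ratio away from 1 even when randomisation has balanced that predictor. Here one covariate is the baseline value of the very variable that is dichotomised.

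The continuous endpoints do not have this difficulty. An adjusted difference in means from a linear model has the same target as the unadjusted difference, so the wording used for the MMRM estimands fits its model. The parallel wording does not fit a logit model.

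At stake is the interpretation of the effect size for two of the three alpha-controlled key secondary endpoints. A reader who forms an odds ratio from the reported proportions would not recover the reported one. The proportion averaged over Weeks 16 and 24, which gives the endpoint its name, is never estimated with an interval.

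**Working it through.** **1. The plan's own figure.** SAP 6.2.2 states more than 95% power for SwCl change: difference -5 mmol/L, SD 14, 275 per group, 10% drop-out, 2-sided 0.05.

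- n = 275 x 0.9 = 247.5 per group
- SE = 14 x sqrt(2/247.5) = 1.258
- 5/1.258 - 1.96 = 2.01, and Phi(2.01) = 97.8%

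The figure reproduces. No response rate, odds ratio or power is stated for the responder endpoints.

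**2. Inputs for the odds ratios.** From the SAP: effect -5 mmol/L and SD of change 14. Assumed, because the documents do not give them: on-treatment baseline SwCl normal with mean m and SD s, slope 1 on baseline, one visit. The planning values belong to the Study 103 change endpoint; carrying them over to the pooled population is a further assumption.

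**3. Formulas.** With post-baseline SwCl = baseline - 5T + N(0, 14) and threshold c:

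- Marginal: P(response | T) = Phi((c - m + 5T)/sqrt(s^2 + 14^2))
- Given baseline b: P(response | T, b) = Phi((c - b + 5T)/14)

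The same 5 mmol/L is divided by 14 given baseline, but by the larger sqrt(s^2 + 14^2) marginally. That fixes the direction of the gap. The conditional odds ratio is exp(beta) from the large-sample logistic fit of response on treatment and b, with b integrated numerically over its distribution.

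**4. Example, m = 50, s = 18.** sqrt(324 + 196) = 22.80.

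| Threshold | Control | Treated | Marginal OR | Conditional OR | Ratio |
|---|---|---|---|---|---|
| <60 | Phi(10/22.80) = 66.9% | Phi(15/22.80) = 74.5% | (0.7447/0.2553)/(0.6695/0.3305) = 1.44 | 1.87 | 1.30 |
| <30 | Phi(-20/22.80) = 19.0% | Phi(-15/22.80) = 25.5% | (0.2553/0.7447)/(0.1902/0.8098) = 1.46 | 1.88 | 1.29 |

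As a rough check, 1.7 x 5/14 = 0.607 and exp(0.607) = 1.84, close to the fitted values.

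**5. Grid, m = 40, 45, 50, 55 and both thresholds.**

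| Baseline SD s | Conditional OR | Marginal OR | Paired ratio |
|---|---|---|---|
| 10 | 1.83-1.96 | 1.61-1.77 | 1.11-1.14 |
| 15 | 1.85-1.92 | 1.49-1.57 | 1.22-1.24 |
| 20 | 1.86-1.90 | 1.39-1.44 | 1.32-1.34 |
| 25 | 1.87-1.89 | 1.32-1.35 | 1.40-1.41 |

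The conditional value barely moves; the assumed baseline SD sets the gap. A separate simulation (mean 45-60, SD 15-20, slope 0.7 or 1.0, 400,000 subjects per scenario) gave conditional 1.85-2.19 against marginal 1.39-1.77, a ratio of 1.15-1.33.

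**6. Does standardising recover the marginal value?** Predicting every subject's probability under each treatment from the fitted adjusted model, averaging, and forming the odds ratio returned the marginal value to within 0.02 in that simulation.

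**7. Is the test affected?** The check was a two-visit logit GEE with log odds ratios averaged over the visits and sandwich standard errors, m = 50, s = 18, 2,000 trials per setting, N = 550 and an assumed pooled N of 950. It used an independence working correlation rather than the planned unstructured one.

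- No effect: adjusted odds ratio 0.99-1.00, rejection 4.8%-5.8%. Monte Carlo SE is sqrt(0.05 x 0.95/2000) = 0.5 points, so this is consistent with 5%.
- 5 mmol/L effect: adjusted odds ratio 1.88-1.91, unadjusted 1.45-1.46; power 85%-98% adjusted, 54%-82% unadjusted.

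**The case against.** **The SAP never says marginal.** It speaks of comparing response rates and then names the adjusted GEE, so one can hold that a covariate-adjusted odds ratio was intended all along. This stands to the extent that the documents leave the target unspecified rather than contradict themselves. A reader might infer that the reported effect is not the estimand and overstates it. That goes too far: overstatement presupposes a marginal target and a non-zero effect, and the conditional odds ratio is a different quantity, not a biased one. Either reading still needs an edit, because the summary as worded does not describe what the model returns.

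**Response rates will be visible.** Counts and proportions are tabulated by visit and group, so a reader can form a crude odds ratio at Weeks 16 and 24. This stands; it would be wrong to say that proportions are not reported. They are crude, separate by visit and without an interval, and their odds ratio will not match the one beside the P value.

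**No decision changes.** The hierarchy uses only the test. This stands. A reader might infer that type I error is at risk; step 7 shows no sign of it, and adjustment adds power.

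**The convergence fallback.** One might argue that the reported value depends on which covariates survive it. The fallback collapses or removes genotype only and then changes the correlation structure. Baseline SwCl, which drives the gap shown here, always stays in. The calculations contain no genotype term and give no size for that effect.

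**The size is assumed.** This stands. The documents give no on-treatment SwCl mean or SD, no response rates and no Study 102 sample size.

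**Conclusion.** The point holds as a mismatch between a summary that is most naturally marginal and an estimator that is conditional on covariates. It applies to both pooled responder key secondary endpoints and to the versions that inherit the model. If there is a treatment effect, the reported odds ratio will lie further from 1 than the odds ratio of the two response rates. Under the stated assumptions the factor is about 1.1 (baseline SD 10) to 1.4 (baseline SD 25). The direction follows from non-collapsibility with a predictive baseline; the factor cannot be fixed from the documents. The hypothesis test and the hierarchy are sound. What needs correcting is the definition and reporting of the effect size: a cheap improvement, worth making because these effect sizes carry formal claims.

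**What to change.** In SAP 8.3.2.2:

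1. Keep the adjusted GEE Wald test as the test in the hierarchy, and label its coefficient as a covariate-conditional odds ratio.
2. From the same fitted model, predict each PFAS subject's response probability under each treatment at Weeks 16 and 24, and average over subjects and over the two visits. Report the standardised response rate per group and the marginal odds ratio formed from those rates, with 95% CIs by delta method or by bootstrap resampling whole subjects.
3. Optionally add the difference in standardised proportions with its CI. The stated summary is an odds ratio, so this goes beyond it.
4. Apply the same to <30 mmol/L and, in the FAS, to the within-study versions.

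Dropping the covariates is not a good alternative, because step 7 shows that it costs power. If the sponsor does intend a conditional target, the estimand summary should be reworded to say so, and the standardised rates remain useful beside it.

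The cost is a few sentences of SAP text and a small amount of programming, with no change to design, alpha or data collection. There are two further downsides: the marginal odds ratio will look less favourable, and it refers to the particular covariate mix of the two pooled studies.

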### **12.3.3.2 Analysis of Secondary Endpoints**

#### **Analysis of Key Secondary Variables**

- Absolute change from baseline in SwCl through Week 24: The analysis of this variable will be based on an MMRM similar to the analysis of the primary endpoint above, with absolute change from baseline in SwCl at Day 15, Week 4, Week 16, and Week 24 as the dependent variable. The primary result obtained from the model will be the estimated treatment difference through Week 24. The LS mean estimate with a 2-sided 95% CI and a 2-sided *P* value will be provided. The estimated within group change from baseline and the treatment difference at each post-baseline visit, obtained from the model, will also be provided.
- Proportion of subjects with SwCl <60 mmol/L through Week 24 (pooled with data from Study VX20-121-102): The response corresponding to SwCl <60 mmol/L through Week 24 based on pooling data from FAS of this study and from Study VX20-121-102 (which has a similar study design and will evaluate CF subjects with other genotypes) will be analyzed. Details of this analysis will be described in the SAP.
- Proportion of subjects with SwCl <30 mmol/L through Week 24 (pooled with data from Study VX20-121-102): The response corresponding to SwCl <30 mmol/L through Week 24 based on data pooled from the FAS of this study and from Study VX20-121-102 will be analyzed. Details of this analysis will be specified in the SAP.

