### **3 INTRODUCTION**

This statistical analysis plan (SAP) is the planned statistical analysis for Study VX20-121-103 (Study 103) and is based on the most recent approved clinical study protocol (CSP), the most recent approved electronic case report form (eCRF), and the most recent eCRF completion guidelines.

Study 103 is a Phase 3, randomized, double-blind, elexacaftor/tezacaftor/ivacaftor (ELX/TEZ/IVA)-controlled, parallel group, multicenter study evaluating the efficacy and safety of vanzacaftor (VX-121)/tezacaftor/deutivacaftor (VNZ/TEZ/D-IVA) in cystic fibrosis (CF) subjects who are homozygous for *F508del* (F/F), heterozygous for *F508del* and a gating (F/G) or residual function (F/RF) mutation, or have at least 1 triple combination responsive (TCR) *CFTR* mutation identified as responsive to ELX/TEZ/IVA and do not have an *F508del* mutation (TCR/non-F). This SAP (Methods) documents the planned final analyses and data presentation for Study 103. For some of these analyses, the Study 103 data are pooled with data from Study VX20-121-102 (Study 102) which is running in parallel with a similar study design and aims to evaluate similar outcomes using a different patient population.

The Vertex Pharmaceuticals Incorporated (Vertex) Biometrics Department will perform the statistical analysis of the efficacy and safety data. SAS® Version 9.4 Software (SAS Institute, Cary, North Carolina, USA) or higher will be used to generate all statistical outputs (tables, figures, listings, and datasets).

The SAP (Methods) will be finalized and approved prior to clinical database lock and treatment unblinding. Any revisions to the approved SAP will be documented and approved in an amendment to the SAP prior to the clinical database lock.

The analysis addressing the pharmacokinetic (PK) objective of the study will be described in the Clinical Pharmacology Analysis Plan which will be developed separately by the Clinical Pharmacology department at Vertex.

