### **7.3 Pooled Full Analysis Set**

The **Pooled Full Analysis Set** (PFAS) will include all randomized subjects from this study (Study 103) and from Study 102 who carry the intended *CFTR* genotype and received at least 1

dose of study drug during the Treatment Period. The PFAS will be used only for pooled analysis of selected endpoints.

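### If the pooled responder model fails to converge, the SAP permits removal of genotype, the only term that separates Study 102 from Study 103, and gives no rule for choosing removal over collapse

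*SAP*

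**What the plan says.** SAP 7.3 defines a pooled set that "will include all randomized subjects from this study (Study 103) and from Study 102". SAP 8.3.2.2 analyses SwCl below 60 mmol/L in that set with a logit GEE. Its terms are treatment, age group, "genotype group (F/MF, F/F, F/G, F/RF, TCR/non-F), visit, and treatment-by-visit interaction", plus continuous baseline ppFEV1 and baseline SwCl. Study is not among them.

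If estimation does not converge, "genotype group will be considered with three levels (F/MF, F/F, and Other) or removed from the model". After that, "if non-convergence persists, an alternative covariance structure like compound symmetry will be used".

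The below-30 mmol/L test takes over the same estimand and analysis (SAP 8.3.2.2). Both tests are in the alpha-controlled hierarchy (SAP 8.3.2.3). The pooled Week 52 analyses in SAP 8.5.2 use a similar model but are outside the hierarchy.

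On Study 102, Protocol 12.3.3.2 says only that it is a trial "which has a similar study design and will evaluate CF subjects with other genotypes". SAP 3 describes it as "running in parallel with a similar study design and aims to evaluate similar outcomes using a different patient population". SAP 6.3 gives Study 103's genotype groups as F/F, F/G, F/RF and TCR/non-F, with 1:1 allocation.

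**The concern.** Subjects were randomised within each trial, so a pooled confirmatory test should compare arms within trial at every step, fallbacks included. The planned model does this through the F/MF level of genotype. One of the two permitted fallbacks deletes that level and puts nothing in its place.

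Two things are at stake. First, the odds ratio would come from a model that does not separate two trials in different populations. Odds ratios are non-collapsible, so its size depends on which prognostic terms are kept. Second, collapse and removal are two different models with two different P values, and the SAP does not say which one to use. Removal may also come before any simplification of the working correlation, a step that would leave the model terms unchanged.

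**Working it through.** **1. Which term identifies Study 102?**

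| Source | Genotype groups |
|---|---|
| Study 103 (SAP 6.3; Protocol 8.1, criterion 5) | F/F, F/G, F/RF, TCR/non-F |
| Pooled GEE (SAP 8.3.2.2) | F/MF, F/F, F/G, F/RF, TCR/non-F |
| Study 102 (Protocol 12.3.3.2; SAP 3) | not listed; other genotypes, different population |

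The pooled list adds one level, F/MF. Since Study 102 enrols genotypes other than those of Study 103, F/MF coincides with Study 102. This is an inference, because Study 102's groups are nowhere listed.

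**2. What does each model keep?**

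| Model | Are the trials separated? |
|---|---|
| Five-level genotype (planned) | yes |
| F/MF, F/F, Other (fallback) | yes |
| Genotype removed (fallback) | no; age group, baseline SwCl and baseline ppFEV1 remain |

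**3. Large-sample check with no covariates.** The plan states no response rate or power for the pooled tests, so there is no figure to reproduce. Assume a true odds ratio of 2 within each trial, control response of 90% in Study 103 and 70% in Study 102, 550 and 400 subjects, and 1:1 allocation in both.

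- Weights: 550/950 = 0.579 and 400/950 = 0.421.
- Treated response: odds 9 × 2 = 18, so 18/19 = 0.947; odds 2.333 × 2 = 4.667, so 4.667/5.667 = 0.824.
- Pooled control: 0.579 × 0.9 + 0.421 × 0.7 = 0.816, odds 4.43.
- Pooled treated: 0.579 × 0.947 + 0.421 × 0.824 = 0.895, odds 8.54.
- Odds ratio ignoring study: 8.54/4.43 = 1.93.

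With Study 102 at 300 to 550 subjects, the result is about 1.98 for control rates of 90%/80%, about 1.93 for 90%/70% and 1.78 to 1.79 for 90%/50%. With a true odds ratio of 1 it stays at 1.00 throughout.

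**4. Simulation of error rates.** One response per subject, adjusted for baseline SwCl, 550 and 400 subjects, both trials 1:1, 1,500 runs per setting. The residual study effect is what remains at a given baseline.

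| Residual study effect (log-odds) | OR, true value 2: study kept / omitted | Type I error: kept / omitted | Power: kept / omitted |
|---|---|---|---|
| 0 | 2.02 / 2.02 | 0.045 / 0.045 | 96.3% / 96.3% |
| -1 | 1.99 / 1.93 | 0.050 / 0.044 | 98.3% / 97.9% |
| -2 | 2.01 / 1.77 | 0.043 / 0.031 | 97.7% / 96.9% |

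**5. Simulation on the mmol/L scale.** From SAP 6.2.2: difference -5 mmol/L, SD 14, and 10% drop-out from 275 per arm. 275 × 0.9 = 247.5, taken as 247, gives 2 × 247 = 494 in Study 103. Assumed: 360 in Study 102, baseline SD 20, one visit. The threshold is 60 mmol/L.

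- Residual shift 0: log odds ratio 0.636 with a study term and 0.635 without; power 85.3% and 85.1%.
- Residual shift 8 mmol/L: 0.629 and 0.601, that is, odds ratios of 1.88 and 1.82; power 84.5% and 83.1%. A separate run gave 0.64 and 0.61, with about 1 point of power lost.
- Residual shift 15 mmol/L: about 3 to 4 points of power lost.

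With 1,500 runs, the Monte Carlo standard error of one power estimate is √(0.845 × 0.155/1500) = 0.009. Power levels depend on the assumed baseline distribution, so the within-row differences are what matter.

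**The case against.** The strongest reply is that the planned model already separates the trials, and so does the first-listed fallback. The issue arises only if the GEE fails to converge and removal is then chosen. The wording could be read as an order, collapse first and remove second, and the trigger is a numerical failure, not a result. The primary MMRM (SAP 8.3.1.3) has the same removal option. All of this stands and limits the weight of the point. It does not supply a rule, though, and in a single-trial model removal costs a covariate, whereas here it also costs the trial identifier.

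A reader might infer that removal means crude pooling with no adjustment. The documents do not support that. Baseline SwCl, the continuous form of the variable being dichotomised, stays in the model with baseline ppFEV1 and age group. These can absorb part of a between-trial difference, although they do not identify the trial.

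A reader might also infer that the confirmatory tests lose error control. They do not under 1:1 allocation: in step 4 type I error was at or below its nominal level. The move of the odds ratio toward 1 is non-collapsibility, not confounding. That protection rests on balance within both trials, and 1:1 is stated only for Study 103. If Study 102 were allocated 2:1, the null odds ratio in step 3 would be 0.71 to 0.88 across the unequal-rate settings. That is hypothetical; nothing in the documents suggests such a ratio.

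**Conclusion.** The gap is real, conditional and small. The only term separating the two trials may be removed on non-convergence, without a rule and without a replacement, in two alpha-controlled tests. With 1:1 allocation in both trials, removal does not inflate type I error. It moves the odds ratio toward 1 and costs about 0 to 4 points of power for residual shifts of 0 to 15 mmol/L.

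This rests on F/MF being equivalent to Study 102 (inferred), on 1:1 allocation in Study 102 (inferred from its similar design), and on assumed values for Study 102's size, the response rates and the residual shift. The mmol/L simulation covers the 60 mmol/L threshold at a single visit; the below-30 test was not simulated. The point is a free improvement, not a challenge to the validity of the pooled tests.

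**What to change.** In SAP 8.3.2.2, replace the removal option so that the fallback reads: collapse genotype to F/MF, F/F and Other *and, if non-convergence persists, reduce it to F/MF versus non-F/MF*; then change the working correlation structure. Equivalently, if genotype is removed, put a study term in its place.

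Do not add study alongside genotype. If F/MF identifies Study 102, the study indicator is collinear with the F/MF level in both the five-level and three-level models and adds nothing.

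Apply the same wording to the below-30 mmol/L test and, for consistency, to the nominal pooled Week 52 analyses in SAP 8.5.2.

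The cost is one phrase, settled before database lock and unblinding. Little is given up. Protocol 9.1 expects about 80% of Study 103 to be F/F, leaving about 550 × 0.20 = 110 subjects across three groups. If those sparse groups cause the failure, collapsing them already deals with it, and a two-level term is unlikely to cause another.
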